7.10.1.5 Self-estimated adherence

Self-estimated adherence will be analysed descriptively by visit (after 1 year and, if sufficient data are available, after 2 years) for each treatment group and in total. T-tests for comparing treatment groups will be performed.

7.10.2 Secondary safety analyses

All-cause mortality or unplanned cardiovascular hospitalizations as recurrent event

All-cause mortality or unplanned cardiovascular hospitalizations will be analysed by Negative Binomial Regression with treatment as factor and data from health insurance funds (yes/no) and time within study as offset variable. The logarithm will be used as link function.

Events regarding hospitalization are recorded in the medical practices (eCRF) and will be provided by health insurance funds. However, health insurance data were not available for all patients included in the study. Differences between patients with and without data from health insurance funds cannot be excluded. Therefore, the analysis will be adjusted for data from health insurance funds (yes/no).

The following SAS code can be used:

```
PROC GENMOD DATA=indata;  
    CLASS treatment;  
    MODEL primsafetyendpoint = treatment ... / LINK=log DIST=negbin  
    OFFSET=log_time  
    LSMEANS treatment / DIFF CL;  
RUN;
```

The results are provided showing parameter estimates, LSMEANS and LSMEAN-differences together with their corresponding p-values and 95% confidence intervals as well as the negative binomial dispersion parameter.

Additionally, the number of deaths and unplanned cardiovascular hospitalizations will be analysed descriptively.

Although statistical guidelines (“Points to consider on adjustment for baseline covariates”) suggest adjusting the primary analysis for all stratification variables of the randomization process, this is omitted. It is desired to get a robust result, if one treatment regimen is favourable to the other across all stratification factors.

Several analyses for sensitivity are performed.

1. The analysis is repeated for the PP population
2. The analysis is repeated, but the characteristics from the randomization process are also included in the analysis model (sex (male vs. female), age (<75 vs. ≥75 years), NYHA functional class (I and II vs. III and IV), PHQ-9 score (score <10 vs. ≥10), diabetes mellitus (yes vs. no). All characteristics are included in the model as covariates at the same time without any interaction terms.
3. There is a Kaplan-Meier analysis for the time to first event (death or unplanned cardiovascular hospitalization, whatever occurs first). If no event is reported, time will be censored at the time of last contact. The median time to event will be displayed together with the 25% and the 75% quartile.

Unplanned cardiovascular hospitalizations (recurrent event, number)

The number of unplanned cardiovascular hospitalizations will be analysed by Negative Binomial Regression with treatment and data from health insurance funds (yes/no) as factor and time within study as offset variable. The logarithm as link function will be used.

Additionally, the number of unplanned hospitalizations and the cumulative number of unplanned cardiovascular hospitalizations per visit will be analysed descriptively by treatment group and in total. Explorative p-values for the difference between treatment groups will be shown. There will be a Kaplan-Meier analysis for the time to first unplanned cardiovascular hospitalization. If no unplanned cardiovascular hospitalization is reported, time will be censored at the time of last contact or death. The median time to unplanned cardiovascular hospitalization will be displayed together with the 25% and the 75% quartile.

Unplanned hospitalizations for heart failure (recurrent event, number)

The number of unplanned hospitalizations for heart failure will be analysed by Negative Binomial Regression with treatment and data from health insurance funds (yes/no) as factor and time within study as offset variable. The logarithm as link function will be used.

Additionally, the number of unplanned hospitalizations for heart failure and the cumulative number of unplanned hospitalizations per visit will be analysed descriptively by treatment group and in total.

The analysis will be adjusted for data from health insurance funds (yes/no).

There will be a Kaplan-Meier analysis for the time to first unplanned hospitalization for heart failure. If no unplanned hospitalization for heart failure is reported, time will be censored at the time of last contact or death. The median time to unplanned hospitalization for heart failure will be displayed together with the 25% and the 75% quartile.

Percentage of days lost due to unplanned cardiovascular hospitalization of any cause or death of any cause

The SECONDARY safety variable is all-cause mortality or unplanned cardiovascular hospitalizations as percentage of days lost due to unplanned cardiovascular hospitalizations or death between baseline (day of randomization) and individual follow up date.

The number of days lost due to death of any cause or unplanned cardiovascular hospitalizations as the fraction of maximum possible days alive and out of hospital will be analysed by a Wilcoxon signed-rank test comparing both treatment groups. Additionally, the number of days lost due to death of any cause or unplanned cardiovascular hospitalizations will be analysed descriptively by treatment group and in total

Percentage of days lost due to hospitalization of any cause or death of any cause

The number of days lost due to hospitalization of any cause or death of any cause as the fraction of actual days alive and out of hospital will be analysed by a two-sided stratified Wilcoxon signed-rank test (van Elteren test) comparing both treatment groups. Additionally, the number of days lost due to hospitalization or death of any cause will be analysed descriptively by treatment group and in total.

The analysis will be adjusted for data from health insurance funds (yes/no).

Unplanned all-cause hospitalizations

The number of unplanned all-cause hospitalizations will be analysed by Negative Binomial Regression with treatment and data from health insurance funds (yes/no) as factor and time within study as offset variable. The logarithm as link function will be used.

Additionally, the number of unplanned all-cause hospitalizations and the cumulative number of unplanned all-cause hospitalizations per visit will be analysed descriptively by treatment group and in total.

There will be a Kaplan-Meier analysis for the time to first unplanned all-cause hospitalization. If no unplanned all-cause hospitalization is reported, time will be censored at the time of last contact or death. The median time to unplanned all-cause hospitalization will be displayed together with the 25% and the 75% quartile.

All-cause mortality

All-cause-mortality (time to death from any cause) will be analysed using the logrank test. The time to death from any cause will be displayed by a Kaplan-Meier curve. The median time to death from any cause will be displayed together with the 95% confidence interval. If no death is reported, time will be censored at the time of last contact. Additionally, the time to death will be analysed descriptively by treatment group and in total.

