### 7.2 Inclusion and Exclusion Criteria

#### 7.2.1 Inclusion Criteria

- Age: 60 years and older
- Diagnosis of chronic heart failure (CHF)
- Stable CHF medication including a diuretic
- Hospitalization for decompensated heart failure within past 12 months OR a value of  $\geq 350$  pg/mL for BNP or  $\geq 1400$  pg/mL for NT-proBNP [22,23]
- Written informed consent

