7.10 Secondary analyses

All parameters will be tested for the ITT population on a two-sided level of significance 5%. All p-values will be interpreted in an exploratory way.

All secondary variables will also be analysed for the PP population. These analyses will be considered as exploratory only.

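### Kaplan-Meier medians and quartiles for time to first hospitalisation treat death as censoring, so they describe hospitalisation as earlier and more frequent than it is

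*SAP*

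**What the plan says.** SAP 7.10.2 applies one censoring rule to three endpoints:

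- First unplanned cardiovascular hospitalisation: "If no unplanned cardiovascular hospitalization is reported, time will be censored at the time of last contact or death".
- First unplanned heart failure hospitalisation: "If no unplanned hospitalization for heart failure is reported, time will be censored at the time of last contact or death".
- First unplanned all-cause hospitalisation: "If no unplanned all-cause hospitalization is reported, time will be censored at the time of last contact or death".

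The reported summary is a set of quantiles. For the cardiovascular endpoint, "The median time to unplanned cardiovascular hospitalization will be displayed together with the 25% and the 75% quartile", and the other two have matching sentences. No cumulative incidence function or other competing-risk method appears in the protocol or the SAP.

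The same section counts death as an event in one time-to-first-event analysis, a sensitivity analysis for the composite: "There is a Kaplan-Meier analysis for the time to first event (death or unplanned cardiovascular hospitalization, whatever occurs first". All-cause mortality has its own Kaplan-Meier curve and logrank test. SAP 7.10 sets the status of all secondary results: "All p-values will be interpreted in an exploratory way".

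**The concern.** Censoring at last contact assumes that the patient could still have the event afterwards, unobserved. That is reasonable for someone who leaves the study and wrong for someone who has died. If the two are handled alike, 1 minus Kaplan-Meier estimates a hospitalisation probability in a world where nobody dies first. It lies above the proportion of patients actually admitted, and its quantiles are reached too soon.

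Deaths before a first admission are plausible here. The inclusion criteria in protocol 7.2.1 set "Age: 60 years and older" and require either a recent decompensation or a raised natriuretic peptide ("Hospitalization for decompensated heart failure within past 12 months OR a value of" the stated cut-offs). The protocol synopsis expects a mean follow-up of 24 months. At stake is whether a reader can take the published median or quartile as the time by which that share of patients had been admitted.

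**Working it through.** **Inputs.** The censoring rule and displayed quantiles come from SAP 7.10.2. Follow-up (mean 24 months, minimum 12) comes from the protocol synopsis. The plan has no figure of its own to reproduce: it states no hospitalisation rate, death rate or event count, and protocol 11.1 powers the study for the primary efficacy variable only. The hazards below are therefore assumptions.

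- h = 0.35 per year: hazard of first hospitalisation.
- m = 0.05, 0.10 or 0.15 per year: hazard of death without a prior qualifying hospitalisation. This is not overall mortality, because a death after a first admission does not compete with that admission.

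**Formulas (constant hazards).**

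- Planned method: 1 − KM(t) = 1 − exp(−h·t); quantile p at −ln(1 − p)/h.
- Actual probability: CIF(t) = h/(h+m) × [1 − exp(−(h+m)·t)]; quantile p at −ln(1 − p(h+m)/h)/(h+m), which exists only if p < h/(h+m).

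**Probability hospitalised.**

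- 1 year: 1 − KM = 1 − exp(−0.35) = 29.5%. CIF at m = 0.05: 0.875 × (1 − exp(−0.40)) = 28.8%; at 0.10: 0.778 × (1 − exp(−0.45)) = 28.2%; at 0.15: 0.70 × (1 − exp(−0.50)) = 27.5%. Excess 0.7, 1.3 and 2.0 points.
- 2 years: 1 − KM = 1 − exp(−0.70) = 50.3%. CIF at m = 0.05: 0.875 × (1 − exp(−0.80)) = 48.2%; at 0.10: 0.778 × (1 − exp(−0.90)) = 46.2%; at 0.15: 0.70 × (1 − exp(−1.00)) = 44.2%. Excess 2.2, 4.2 and 6.1 points.

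**Quantiles, in years.**

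| Quantile | Kaplan-Meier | CIF, m = 0.05 | CIF, m = 0.10 | CIF, m = 0.15 |
|---|---|---|---|---|
| 25% | 0.82 | 0.84 | 0.86 | 0.88 |
| Median | 1.98 | 2.12 | 2.29 | 2.51 |
| 75% | 3.96 | 4.86 | 7.40 | not reached |

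At m = 0.15 the cumulative incidence cannot exceed 0.35/0.50 = 70%, so a 75% quartile does not exist.

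**Wider range.** With first hospitalisation at 10 to 50% per year and death without prior hospitalisation at 3 to 20% per year (each converted to a hazard by −ln(1 − rate)), the excess was positive in every combination: 0.1 to 4.6 points at 1 year and 0.5 to 11.5 points at 2 years.

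**Does the direction need independence?** Simulation at 25% and 10% per year, with administrative censoring uniform between 1 and 3 years, gave 2-year values of 43.8% (1 − KM), 39.9% (Aalen-Johansen) and 39.9% (true proportion). With a shared frailty of variance 1 linking death and hospitalisation they were 34.5%, 32.1% and 32.1%. The bias kept its direction, and Aalen-Johansen matched the truth both times.

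**The case against.** The case for leaving the plan alone has several parts, and most of them limit the point without removing it.

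- **Other analyses already include death.** Time to first hospitalisation is not a listed variable. The main comparison for each hospitalisation endpoint is negative binomial regression. Death enters the primary safety variable, days lost, mortality and the composite Kaplan-Meier. This stands, with one gap: the composite covers cardiovascular hospitalisation only, so heart failure and all-cause hospitalisation have no time-to-first-event analysis that counts death.
- **Death-censored Kaplan-Meier is a legitimate cause-specific summary.** It is, if labelled so. The SAP gives no such label and reports medians and quartiles, which readers will take as times by which patients were admitted.
- **The quantile most likely to be estimable moves least.** Under the hazards above the 25% quartile shifts by only 2 to 3 weeks for m = 0.10 to 0.15. The median falls at or beyond the mean follow-up and the 75% quartile far past it. This stands.
- **The rates are assumed.** They are, and one set of hazards cannot fit three endpoints whose rates must differ. Protocol 7.2.2 also excludes patients with a life expectancy under 6 months, which should lower early mortality.

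Two stronger readings are tempting. A reader might infer that the comparison between arms is distorted. The SAP specifies no between-arm test for these three analyses (the logrank test is for mortality), and censoring at death remains valid for comparing cause-specific hazards. A reader might also infer that misleading hospitalisation curves are planned. The SAP names a curve only for all-cause mortality; for hospitalisation it commits to an analysis with quantiles, and its table and figure shells are in a separate document. The documented problem is the quantiles, together with any probability read from the same analyses.

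**Conclusion.** The point holds for the displayed medians and quartiles of the three hospitalisation endpoints. Whenever deaths precede a first admission while other patients are still at risk, these quantiles come too early and the implied probabilities are too high. That direction does not depend on the assumed rates or on independence of death and hospitalisation.

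The size does depend on assumptions. At the base-case hazards it is modest at 1 year, larger at 2 years, and greatest for the upper quantiles, which follow-up may not reach anyway. If few patients die without a prior admission, the effect is negligible.

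Severity is minor. The outputs are secondary and exploratory, and the documents give no ground for extending the criticism to the primary safety analysis or the negative binomial models.

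**What to change.** In SAP 7.10.2, for first unplanned cardiovascular, heart failure and all-cause hospitalisation:

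1. Report Aalen-Johansen cumulative incidence by arm, with death before the first qualifying admission as a competing event.
2. Take the median and quartiles from that estimate, and state that a quantile is not reached where that is so.
3. If death-censored Kaplan-Meier output is kept, label it as cause-specific and not as a probability of hospitalisation.
4. Leave Kaplan-Meier in place for all-cause death and for the composite that includes death.

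The cost is a few sentences of SAP text and some programming. Dates of death are already collected (protocol 8.2.5, SAP 5.4.1), and the estimator is available in SAS 9.4, the version named in SAP section 8. No new data are needed.

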7.11 Subgroup analyses

Exploratory subgroup analyses will be performed for the primary efficacy and primary safety variables. Additionally, subgroup analyses for the PDC of each drug class, the mean PDC $\geq 80\%$, all-cause mortality or unplanned cardiovascular hospitalizations as recurrent event, unplanned cardiovascular hospitalizations as recurrent event, and all-cause mortality will be performed.

Each subgroup and the corresponding interaction with treatment group will be included into the analysis model (the PDC of each drug class will be analysed by an ANOVA,

for the mean PDC $\geq 80\%$ a logistic regression model will be used). The following subgroups are planned:

- Minimization-criteria:
 - o Sex (male/female),
 - o Age (≤ 75 , > 75 years),
 - o NYHA functional class (I and II, III and IV),
 - o PHQ-9 (depression score < 10 , ≥ 10),
 - o Diabetes mellitus (yes/no),
- Time between last heart failure hospitalization and randomization (< 3 months vs. ≥ 3 months) Number of different drug substances (median at randomisation), as an indicator of the level of illness burden
- Number of different co-morbidities (median at randomisation), as a further indicator of the level of illness burden
- Heart failure medication at baseline (BB versus BB plus ACEi/ARB, BB plus ACEi/ARB versus BB plus ACEi/ARB/MRA) (subpopulations)
- Heart rate at baseline (≤ 75 vs. > 75 min^{-1})
- QoL score (MLHFQ Median)
- HFrEF vs. HFmrEF/HFpEF (LVEF $< 40\%$ vs. $\geq 40\%$)

The subgroup analyses will be displayed by the interaction term as well as descriptive statistics by subgroup.

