## 11 Biometrics

### 11.1 Sample Size

[figure not shown]

Figure 2: Sample Size Calculation

The primary efficacy variable is adherence to CHF medication. We conservatively assume an improvement of the summary PDC  $\geq 10\%$  in the intervention group compared to usual care as clinically relevant.

Assuming a mean PDC in the year before randomization of approximately 0.7 a sample size of  $N=176$  patients (88/group) is needed to detect a 10% (SD 22%) improvement between the intervention group and the usual care group with a power of 85% and an alpha of 5%. Assuming a dropout and lost to follow up of 30%  $N=248$  patients have to be enrolled in the study.

The study is powered for the primary efficacy variable only.

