### 11.4.5 Subgroup Analyses

Several pre-specified subgroups will be explored.

The following subgroups are planned:

- Minimization-criteria:
  - Sex (male/female)
  - Age (<75, ≥75 years)
  - NYHA functional class (I and II, III and IV)
  - PHQ-9 (depression score <10, ≥10)
  - Diabetes mellitus (yes/no)
  - The study region will be omitted since this may lead to an over determination of the analysis model.
- Time between last heart failure hospitalization and randomization (≤ 3 months vs. > 3 months before study)
- Number of different drug substances (median at randomization), as an indicator of the level of illness burden
- Number of different co-morbidities (median at randomization), as a further indicator of the level of illness burden
- Heart failure medication at baseline (BB versus BB plus ACEi/ARB, BB plus ACEi/ARB versus BB plus ACEi/ARB/MRA) (subpopulations)
- Heart rate at baseline (≤ 75 vs. > 75 min)
- QoL score (MLHFQ Median)
- HFrEF vs. HFmrEF/HFpEF (LVEF <40% vs. ≥ 40%)

Each subgroup and the corresponding interaction with treatment group will be included into the analysis model (the PDC of each drug class will be analysed by an ANOVA, for the mean PDC ≥80% a logistic regression model will be used).

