1.2 Sample size considerations

Assuming a baseline PDC for cardiovascular medication of 0.7 and a standard deviation of the PDC of 0.22 a sample size of N=176 (88/group) patients is needed to detect a 10% difference between the intervention group and the usual care group with a power of 85% and an alpha of 5%. Assuming a dropout and lost to follow-up of 30% N=248 patients have to be enrolled in the study. The planning is based on a two-sided t-test and performed by means of SAS Version 9.4.

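### The treatment interactions for number of drug substances, number of co-morbidities and MLHFQ score are tested only as above or below the sample median; a full-scale term alongside would recover information if the effect changes gradually

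*SAP*

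**What the plan says.** SAP 7.11 lists three subgroups defined by a median:

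- for medicines, the entry reads "Number of different drug substances (median at randomisation), as an indicator of the level of illness burden"
- for concurrent diagnoses, a parallel entry reads "Number of different co-morbidities (median at randomisation), as a further indicator of the level of illness burden"
- the MLHFQ score, also at its median ("QoL score (MLHFQ Median").

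Protocol 11.4.5 has the same three entries, for example "Number of different drug substances (median at randomization), as an indicator of the level of illness burden". The SAP then states: "Each subgroup and the corresponding interaction with treatment group will be included into the analysis model". It names ANOVA for the PDC of each drug class and logistic regression for mean PDC of at least 80%, and adds recurrent-event outcomes, for which SAP 7.10.2 specifies negative binomial regression. Results are to be shown by the interaction term and by descriptive statistics within subgroups.

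The full-scale values exist. SAP 5.3 derives the number of drug substances from the medication plan and records diagnoses individually. SAP 5.8.2 scores the MLHFQ total from 0 to 105.

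The status of these analyses is explicit. SAP 7.11 says: "Exploratory subgroup analyses will be performed for the primary efficacy and primary safety variables". Protocol 11.1 says: "The study is powered for the primary efficacy variable only".

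**The concern.** The two counts are described as indicators of how heavy the illness burden is, which is a graded quantity. The tested term reduces each to two groups, so patients just either side of the median are treated as opposites and differences within each half are ignored.

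The cut is read here as the median of the recruited sample, so its value depends on who was enrolled and does not transfer to another population. The documents give no basis for it. By contrast, SAP 5.8.4 ties the PHQ-9 cut of 10 to signs of depression, and SAP 5.3 ties LVEF below 40% to HFrEF. For MLHFQ, the SAP has its own fixed bands (below 24, 24 to 45, above 45) but does not use them in 7.11. Nor does the plan say which side takes patients who lie exactly on the median, and with counts there may be many.

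At stake is how well the trial can explore whether the intervention works better in patients with a heavier medication or illness burden. Interaction power was not planned for, which is a reason not to discard information already collected.

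**Working it through.** **The plan's own figure.** SAP 1.2 plans for a difference of 0.10 and "a standard deviation of the PDC of 0.22", two-sided 5%, 85% power. Normal approximation: 2 × (1.960 + 1.036)² × 0.22² / 0.10² = 86.9, so 87 per arm. The exact t calculation gives 88 per arm (power 85.05%), which agrees with N = 176. The documents give no interaction power to reproduce.

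**Inputs.** ITT 110 and 127 (SAP 2.2); SD 0.22 (SAP 1.2); two-sided 5%. Assumed: a standardised, roughly normal modifier, and a treatment effect on PDC that changes linearly by d per SD of the modifier.

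**Information kept.** This is the squared correlation between the modifier and its above-median indicator. For a normal modifier it is 2/π = 0.637, so about 36% is lost. Other assumed shapes lose:

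- 25% (uniform)
- 31% (bounded, mildly skewed score)
- 35–38% (counts with mean 4 to 8)
- 45% (gamma with shape 2)
- 52% (exponential).

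**Power.** Full-scale term: SE = 0.22 × √(237 / (110 × 127)) = 0.22 / √58.945 = 0.02865. Power = Φ(d/SE − 1.96) plus the opposite tail. For the split, d/SE is multiplied by √(2/π) = 0.798. At d = 0.05, d/SE = 1.745, giving 41.5%; for the split, 1.392, giving 28.6%.

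| d (PDC per SD) | Full scale | Median split | Loss (points) |
|---|---|---|---|
| 0.02 | 10.7% | 8.6% | 2.1 |
| 0.04 | 28.7% | 20.0% | 8.7 |
| 0.05 | 41.5% | 28.6% | 12.9 |
| 0.075 | 74.5% | 55.1% | 19.3 |
| 0.10 | 93.7% | 79.5% | 14.2 |
| 0.15 | 99.9% | 98.7% | 1.3 |

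Simulated trials with the same group sizes and SD agree: for a normal modifier, about 42% v 29% at d = 0.05 and 77% v 58% at 0.08. For a gamma modifier with shape 2 at d = 0.08 they give about 77% v 54%, a loss of about 23 points. Type I error is about 5% for both tests.

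**Reversed case.** If the effect is a step of size 2d at the median, the split fits and the full-scale term does not. Simulated power, full scale v split, is 21% v 28% at d = 0.04 and 59% v 75% at d = 0.08. If the effect saturates, the two are about equal.

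**Ties.** For a count with an assumed mean of 4 to 8, putting patients at the median in the lower group makes that group about 59–63% of the sample. Putting them in the upper group leaves about 43–45%.

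**The case against.** The strongest reply is that the analyses are exploratory and carry no power claim, and that a pre-specified median split shown with an interaction term is a readable convention. That stands, and it limits the point to an inexpensive improvement.

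Second, the direction of the gain rests on linearity, which the documents support no more than they support a step. That also stands, and it is why the full-scale term should be added and not substituted.

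Third, the calculation uses the SD planned for overall PDC and all 237 ITT patients. The named ANOVA is for class PDC, which covers only patients prescribed that class, and SAP 5.5 says PDC cannot be calculated after withdrawal of consent. Usable numbers and absolute powers will be lower. The fraction of information lost depends on the modifier's shape, not on the sample size.

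Fourth, the tests named for the primary efficacy variable (van Elteren), the primary safety variable (Wilcoxon) and mortality (logrank) have no place for a continuous modifier. This is correct, and the fix is confined to the regression models.

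Fifth, heart rate at 75 and time since hospitalization at 3 months are also dichotomised without a stated reason. True, but those cuts are fixed in advance and do not move with the sample.

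**Conclusion.** The point holds as a minor efficiency issue. Three graded baseline measures enter the interaction test only as above or below the sample median, with no stated basis and no full-scale counterpart. Given a linear change in effect and a roughly normal modifier, about 36% of the information is lost. The cost in interaction power runs from about 2 points for a small interaction to about 19 at its greatest, and falls again for very large interactions. A skewed modifier can take it to about 23 points.

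The larger losses need strong interactions. At d = 0.075 with a mean effect of 0.10, the benefit would be 0.025 at one SD below the mean and 0.175 at one SD above.

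A reader might infer that a loss of about a third of the information always costs at least 8 points and may cost 24. The documents give no interaction size or distribution to support such a range: smaller interactions cost less than 8, and losses above about 19 require a skewed modifier that loses more than a third. A reader might also infer that the full-scale test is always better, or that the trial's conclusions are weakened. Neither follows: a step at the median favours the split, and no confirmatory result depends on these tests.

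**What to change.** In SAP 7.11, for number of drug substances, number of co-morbidities and MLHFQ total, add the full-scale baseline value and its product with treatment to the regression models already planned: ANOVA for class PDC (which becomes ANCOVA for this term), logistic regression for mean PDC of at least 80%, and negative binomial regression for the recurrent-event outcomes. Report the p-value of the product term, and the treatment effect with its 95% CI at the 25th and 75th percentiles of the modifier. Keep the pre-specified median split alongside, and state which group takes patients at the median. Amend Protocol 11.4.5 to match, before the final analysis. The other subgroup cuts can stay as they are.

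The cost is a short amendment to both documents, a few model terms and no new data. The downside is one more exploratory test per variable in each model, resting on an assumption of linearity; the retained split gives a rough check on that.
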